12.1 Pre-Treatment Evaluations (Screening)

The following must be collected/ performed within 28 days prior to Cycle 1, day 1 of treatment. Clinical and laboratory evaluations performed as part of routine standard of care do not need to be repeated if performed within the appropriate window.

- Complete medical history, disease history and prior medical treatments
- Demographic data (age, gender, and race)
- Height
- Weight
- Vital signs (V/S)
 - Oral temperature
 - Blood pressure
 - Heart rate
- Complete physical examination (PE)
- ECOG Performance Status (PS)
- 12-Lead Electrocardiogram (ECG)
- Urine or serum pregnancy test for women of child-bearing potential (WoCBP)
- Complete Blood Count (CBC) with differential (diff)
- Coagulation studies:
 - PT/INR,
 - aPTT
- Comprehensive Serum Chemistry Panel (see Section 10.2.1 for hepatic toxicity guidelines)
 - Albumin,
 - Alkaline phosphatase (alk phos),
 - Total bilirubin,
 - Calcium (Ca),
 - Chloride (Cl),
 - Creatinine,
 - Potassium (K),
 - Total Protein,
 - SGOT (AST),
 - SGPT (ALT),
 - Sodium (Na),
 - Blood urea nitrogen (BUN),
 - Liver function tests (LFTs),
- Thyroid Tests
 - T3
 - T4
 - TSH
- Alpha-fetoprotein (AFP)
- Lipase,
- Amylase and,
- Hepatitis B Virus (HBV) Testing (see Section 10.2.1 for hepatic toxicity guidelines)

- HBsAg,
- HBsAb,
- anti-HBc antibody,
- HBeAg
- Hepatitis C Virus (HCV) Testing (see Section 10.2.1 for hepatic toxicity guidelines)
 - anti-HCV
- Urinalysis (U/A)
- Correlative Studies (See Section 1.5 and 13.0)
- Imaging Studies: Imaging studies for tumor assessment for all known sites of disease, (including triple phase CT or MRI of abdomen with contrast)
- Baseline symptoms

12.2 Evaluations on Treatment

Collection of Concomitant Medications and Adverse Events (AEs) should occur throughout the study, as described. Any SAE, or follow up to a SAE, including death due to any cause other than progression of the cancer under study that occurs to any subject from the time the consent is signed through 90 days following end of treatment, or the initiation of new anti-cancer therapy, whichever is earlier, whether or not related to the Merck product, must be reported within 24 hours to the Sponsor and within 2 working days to Merck Global Safety. All subjects with SAEs must be followed up for outcome. (See Section 15.0 and Appendix A for details).

12.2.1 Day 1 (±3 days, unless otherwise specified), all Cycles: Trial Treatment Administration

- Medical History
- Complete PE
- ECOG PS
- V/S
 - Oral temperature
 - Blood pressure
 - Heart rate
- Weight
- CBC with diff
- Comprehensive Serum Chemistry Panel (see Section 10.2.1 for hepatic toxicity guidelines)
 - Albumin,
 - Alkaline phosphatase (alk phos),
 - Total bilirubin,
 - Calcium (Ca),
 - Chloride (Cl),
 - Creatinine,

- Potassium (K),
- Total Protein,
- SGOT (AST),
- SGPT (ALT),
- Sodium (Na),
- Blood urea nitrogen (BUN),
- Liver function tests (LFTs),
- Alpha-fetoprotein (AFP)
- Lipase and amylase, only if clinically indicated
- Thyroid Tests
 - T3
 - T4
 - TSH
- HBV/ HCV Testing (if tested positive at screening)
 - See Section 10.2.1 for hepatic toxicity guidelines
- Correlative Studies (Optional, See Section 1.5 and 13.0)
- *(Imaging studies for tumor assessment for all known sites of disease (including CT or MRI of abdomen with contrast): the same method of assessment and technique used at baseline will be used during treatment and follow-up. Imaging studies will be done every 3 cycles (after every 9 weeks, ±9 days) from the date of Enrollment, timed to coincide with the end of the prior treatment cycle.)*

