3.0 ENDPOINTS

3.1 Primary endpoints

- Disease control rate (DCR) will be calculated per RECIST 1.1, as the proportion of patients with best overall response of complete response (CR), partial response (PR) or stable disease (SD) that is maintained for at least 8 weeks.
- Treatment-related adverse events (AEs) including serious adverse events (SAEs). AEs will be assessed by and assigned severity using the National Cancer Institute Common Terminology Criteria for Adverse Events (NCI CTCAE), Version 4.03.

3.1.1 Evaluable:

- Evaluable for DCR: Eligible subjects who receive at least one dose of pembrolizumab, have measurable disease at baseline, and have at least one post-baseline disease response assessment.
- Evaluable for Safety: Eligible subjects who receive at least one dose of pembrolizumab.

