12.0 SCHEDULE OF CLINICAL & LABORATORY EVALUATIONS

Prior to performing any study-specific procedures or evaluations, written informed consent and authorization for the use of protected health information (HIPAA) must be obtained in accordance with all applicable policies, regulations and laws.

Correlative evaluations (optional) will also be performed at specified visits. Please refer to Section 1.5 and 13.0 CORRELATIVE STUDIES for details.

Imaging studies should be done *every 3 cycles (every 9 weeks, ±9 days)* from the date of Enrollment timed to coincide with the end of the prior treatment cycle; assessing all known sites of disease using the same type(s) of scan(s) that was/were performed at baseline.

All evaluations should be completed as detailed below, prior to the administration of trial treatment on Day 1 of each cycle. All evaluations will be administered on an outpatient basis.

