14.5.4 Evaluation of Best Overall Response

The best overall response is the best response recorded from the start of the treatment until disease progression/recurrence or non-protocol therapy (taking as reference for progressive disease the smallest measurements recorded since the treatment started). The patient’s best response assignment will depend on the achievement of measurement criteria.

Target Lesions	Non-Target Lesions	New Lesions*	Best Overall Response	Remarks
CR	CR	No	CR	Confirm by repeat assessments ≥ 4 weeks after criteria for response are first met.
CR	Non-CR/Non-PD***	No	PR	
CR	Not evaluated	No	PR	
PR	Non-PD***/not evaluated	No	PR	

SD	Non-PD ^{***} /not evaluated	No	SD	Follow-up assessments must have met SD criteria at least once ≥8 weeks from study entry.
PD	Any	Yes or No	PD	
Any	PD ^{**}	Yes or No	PD ^{***}	
Any	Any	Yes	PD	No prior SD, PR or CR

* See RECIST 1.1 manuscript for further details on what is evidence of a new lesion.
 
** In exceptional circumstances, unequivocal progression in non-target lesions may be accepted as disease progression.
 
*** PD in non-target lesions should not normally trump target lesion status. It must be representative of overall disease status change, not a single lesion increase. Please refer to the Evaluation of Non-Target Lesions – Progressive Disease section for further explanation.
 
 • Patients with a global deterioration of health status requiring discontinuation of treatment without objective evidence of disease progression at that time should be reported as “symptomatic deterioration.” Every effort should be made to document the objective progression even after discontinuation of treatment. • In some circumstances, it may be difficult to distinguish residual disease from normal tissue. When the evaluation of CR depends on this determination, it is recommended that the residual lesion be investigated (fine needle aspirate/biopsy) before confirming the CR status. 				

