14.5.5 Duration of Response

Duration of Overall Response

The duration of overall response is measured from the time measurement criteria are met for CR or PR (whichever is first recorded) until the first date that recurrent or progressive disease is objectively documented (taking as reference for progressive disease the smallest measurements recorded since the treatment started).

The duration of overall CR is measured from the time measurement criteria are first met for CR until the first date that progressive disease is objectively documented.

Duration of Stable Disease

Stable disease is measured from the start of the treatment until the criteria for progression are met, taking as reference the smallest measurements recorded since the treatment started, including the baseline measurements.

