14.6 Disease Control Rate (DCR)

DCR is the proportion of patients whose best overall response per RECIST criteria is complete response (CR), partial response (PR), or stable disease (SD). Disease control must be confirmed by repeat assessments performed at an interval of no less than 4 weeks for CR and PR. For SD, disease control must be confirmed by repeat assessments performed at an interval of no less than 8 weeks.

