16.0 STATISTICAL CONSIDERATIONS

16.1 Objectives and Endpoints

This is a single-arm phase II trial of Pembrolizumab (Keytruda®) in patients with advanced, unresectable hepatocellular carcinoma. The primary objective is to assess its therapeutic efficacy in patients with unresectable hepatocellular carcinoma (HCC). The

primary endpoint is disease-control rate (DCR) defined as the proportion of patients achieving a best overall response of either a CR, PR or SD (that is maintained for at least 8 weeks).

Secondary endpoints include progression-free survival (PFS), overall survival (OS), objective response rate (ORR), duration of response (DOR), and toxicity profile of Pembrolizumab. We will also evaluate the expression levels of PD-L1 in tumor tissue, as well as serum titers of hepatitis B or C in patients with hepatitis B or C, respectively, for whom specimens are available.

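### The first-scan window opens at day 54, two days before stable disease can count toward the primary endpoint, and the sections that define stable disease do not agree

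*Combined protocol and SAP*

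**What the plan says.** **Scan schedule.** Section 12.2.1 states "Imaging studies will be done every 3 cycles (after every 9 weeks, ±9 days) from the date of Enrollment", adding "timed to coincide with the end of the prior treatment cycle". Section 12.0 and calendar footnote I say the same. Section 14.1 gives 9 weeks ±9 days but names no starting point.

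**Primary endpoint.** Section 3.1 counts complete response (CR), partial response (PR), or "stable disease (SD) that is maintained for at least 8 weeks". Section 16.1 repeats the 8-week minimum. Neither says when the 8 weeks start.

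**How SD is established.** Three sections give three rules:
- 14.5.4 (best overall response table): "Follow-up assessments must have met SD criteria at least once ≥8 weeks from study entry".
- 14.5.5: "Stable disease is measured from the start of the treatment until the criteria for progression are met".
- 14.6 (the DCR section): "For SD, disease control must be confirmed by repeat assessments performed at an interval of no less than 8 weeks".

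**Where it is used.** Section 16.2 stops the trial if 2 or fewer of 14 patients have disease control, and declares success at 9 or more of 28. Section 17.2.3 refers the stage 1 determination to section 14.5, which contains the 8-week test.

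**The concern.** The window for the first scan opens before the day on which that scan can satisfy the endpoint. Nothing in the protocol sets a later earliest day or asks for a repeat scan when SD is seen before 8 weeks. Take a patient with SD on day 54 and progression at the second scan, around week 18. Under 14.5.4 that patient has no qualifying SD assessment and is a failure. With the first scan on day 56 and the same disease course, the patient is a success. Both decisions of the trial rest on this count.

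The start dates also differ: Enrollment for scans, study entry in 14.5.4, and start of treatment in 14.5.5 and for progression-free survival (PFS) in 3.2. Section 14.6 adds an interval between assessments that compliant scans need not reach. Two people classifying the same patient from different sections could disagree.

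**Working it through.** **1. The plan's own design figures.** Inputs from 16.2: null DCR 18%, alternative 43%, n1 = 14, stop at ≤2, n = 28, success at ≥9.

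P(stop at stage 1) = P(X1 ≤ 2), with X1 ~ Bin(14, p). P(success) = Σ over x = 3 to 14 of P(X1 = x) × P(X2 ≥ 9 − x), with X2 ~ Bin(14, p).

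| True DCR | Stop at stage 1 | Declare success |
|---|---|---|
| 18% | 52.6% | 4.95% |
| 43% | 2.4% | 90.5% |

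These agree with the stated 53%, 2%, 5% and 90%. The sample size is correct; the issue is how the endpoint is ascertained.

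**2. Day count.** Nominal first scan: 9 × 7 = 63. Window: 63 − 9 = 54 to 63 + 9 = 72, which is 19 days. SD minimum: 8 × 7 = 56. If study entry is Enrollment, days 54 and 55 are too early: 2/19 = 10.5% of the window.

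**3. Who is affected.** Only patients with SD at an early first scan who have no later SD scan, through progression, death, withdrawal or no further imaging. Section 14.5.4 asks for SD at least once, so a patient still stable at the second scan counts. CR and PR have their own 4-week confirmation rule.

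**4. Effect on the decisions (illustration).** Let s be the share of controlled patients with SD at the first scan only. The documents do not give it; 20% to 40% is assumed. Scans are also assumed to be spread evenly over the 19 days. Recorded DCR = 0.43 × (1 − s × 2/19).

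| s | Recorded DCR | Stop at stage 1 | Power |
|---|---|---|---|
| 0 | 43.0% | 2.4% | 90.5% |
| 20% | 42.1% | 2.8% | 88.8% |
| 30% | 41.6% | 3.0% | 87.9% |
| 40% | 41.2% | 3.3% | 86.9% |

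Misclassification runs one way, from success to failure. The recorded DCR can only fall, so type I error is not inflated.

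**5. If the 8 weeks run from first dose instead.** With Enrollment g days before first dose, the earliest scan is day 54 − g on the treatment clock, and 2 + g of the 19 days are too early: 5 of 19 at g = 3 and 9 of 19 at g = 7. The documents do not give g.

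**6. The 14.6 interval.** The second scan is due at 126 ± 9, days 117 to 135. Compliant successive scans can be 117 − 72 = 45 to 135 − 54 = 81 days apart. Two compliant SD scans can therefore miss a 56-day interval.

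**The case against.** The case for leaving this alone has several parts.

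- **It is a two-day edge.** This is correct on the most natural reading. Section 6.0, headed Enrollment Procedures, describes enrolling as entering a patient, so study entry in 14.5.4 probably is Enrollment, and any gap before first dose then cancels.
- **Scans are tied to cycle end.** The end of cycle 3 is nominally day 63 from first dose. That makes days 54 and 55 less likely than an even spread implies, so the table in the working probably errs high. It does not withdraw the ±9 days.
- **Section 14.5.5 would rescue the example patient.** SD on day 54 with progression near day 126 lasts well over 8 weeks when measured from treatment start to progression. That is true, and it shows that the classification depends on the section applied. Section 17.2.3 points to 14.5, which holds both rules.
- **Under 14.6 the contrast may vanish.** If 14.6 requires two on-study scans at least 8 weeks apart, SD on day 56 followed by progression at the second scan also fails. This stands, and it is a reason to reconcile 14.6 in the same edit.

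A reader might infer a much larger loss, for example power of 74.8% with a 7-day gap and s = 30%. The documents do not support that figure. It joins the scan test of 14.5.4 to the treatment start of 14.5.5, a combination that no section states. It needs a gap that is not given. It also spreads scans over treatment days 47 to 65, although most of the early ones would not fall at the end of a cycle.

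A reader might also infer that dose holds delay scans and lengthen PFS, because the same sentence counts both cycles and weeks. The two counts do diverge after a hold, but a scan weeks late would breach the stated ±9-day window, and PFS is a secondary, descriptive endpoint in a single arm.

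**Conclusion.** The point holds. A first scan that complies with 12.0, 12.2.1 and footnote I can fall up to two days before SD can count under 14.5.4, and nothing else in the protocol corrects for it. The effect is modest: power of about 87-89% against 90.5%, and stage 1 stopping of about 3% against 2.4% at a true DCR of 43%. These figures assume that study entry is Enrollment, that scans are evenly spread, and that 20% to 40% of controlled patients have SD at the first scan only. The loss is larger if the 8 weeks run from first dose and Enrollment comes earlier, but its size cannot be stated from the documents. The bias is toward a lower DCR.

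The unreconciled SD rules matter at least as much as the two days, because they leave the classification of some patients open. Severity: should-fix. It touches the primary endpoint and costs almost nothing to repair, but it does not undermine the design.

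**What to change.** 1. In 12.0, 12.2.1, calendar footnote I and 14.1, schedule imaging every 9 weeks by calendar from Cycle 1 Day 1. Give the first scan a window of -7/+9 days (63 − 7 = 56), so that none falls before day 56. Later scans may keep ±9 days.
2. In 14.5.4, replace study entry with Cycle 1 Day 1, so that scans, SD and PFS share one start date.
3. Reconcile 3.1, 14.5.4, 14.5.5, 14.6 and 16.1 to one rule: SD counts toward DCR if its criteria are met on at least one scan 56 days or more after Cycle 1 Day 1. Replace the 14.6 requirement for SD assessments 8 weeks apart with this rule; otherwise compliant scans 45 days apart would still miss it.

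Cost: wording changes, and two fewer days of early flexibility for the first scan. No scans or patients are added, and the sample size and decision boundaries stay as they are.

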12.3 Off-Treatment Evaluations

The following assessments must be performed at the Off-Treatment visit (±5 days).

- Medical History
- Complete PE
- V/S
- Weight
- ECOG PS
- CBC with diff
- Comprehensive Serum Chemistry Panel
 - Albumin,
 - Alkaline phosphatase (alk phos),
 - Total bilirubin,
 - Calcium (Ca),
 - Chloride (Cl),
 - Creatinine,
 - Potassium (K),
 - Total Protein,
 - SGOT (AST),
 - SGPT (ALT),

- Sodium (Na),
- Blood urea nitrogen (BUN),
- Liver function tests (LFTs),
- Alpha-fetoprotein (AFP)
- Lipase and amylase, only if clinically indicated
- Thyroid Tests
 - T3
 - T4
 - TSH
- Correlative Studies (Optional, See Section 1.5 and 13.0)
- *Imaging studies for tumor assessment for all known sites of disease (including CT or MRI of abdomen with contrast): the same method of assessment and technique used at baseline will be used during treatment and follow-up.*

12.4 30 Days After Off Treatment (OT) Safety Evaluations

The following safety assessments must be performed at 30-days (+ 5 days) after Off Treatment date.

- Coagulation studies:
 - PT/INR,
 - aPTT
- Comprehensive Serum Chemistry Panel
 - Albumin,
 - Alkaline phosphatase (alk phos),
 - Total bilirubin,
 - Calcium (Ca),
 - Chloride (Cl),
 - Creatinine,
 - Potassium (K),
 - Total Protein,
 - SGOT (AST),
 - SGPT (ALT),
 - Sodium (Na),
 - Blood urea nitrogen (BUN),
 - Liver function tests (LFTs),
- Alpha-fetoprotein (AFP)
- Lipase and amylase, only if clinically indicated
- Thyroid Tests
 - T3
 - T4
 - TSH
- Correlative Studies (Optional, See Section 1.5 and 13.0)

- *(Any SAE, or follow up to a SAE, including death due to any cause other than progression of the cancer under study that occurs to any subject from the time the consent is signed through 90 days following end of treatment, whether or not related to the Merck product, must be reported within 24 hours to the Sponsor and within 2 working days to Merck Global Safety. All subjects with SAEs must be followed up for outcome. (See Section 15.0 and Appendix A for details).)*

12.5 Follow-up Evaluations

For patients without documented evidence of objective disease progression the following assessments should be performed every 12 weeks until documented disease progression, death, withdrawal of consent, or end of study, whichever occurs first. A *telephone call* to the patient and/or the patient's family may be made to evaluate the patient's status on the following:

- Post-study anticancer therapy status
- Survival status
- Following confirmed disease progression or initiation of new anti-cancer therapy, survival will be assessed (at a minimum) by telephone contact every 12 weeks (± 2 weeks)."

12.6 Calendar of Clinical and Laboratory Evaluations

	Screening	Treatment Cycle(s) q21 days	Off Treatment ±5 days	Safety Evaluation	Follow-Up
	≤28 days prior ^A	Day 1 (±3 days unless specified)		30-days (+5 days) after Off Treatment	every 12 weeks ^K
ICF	X				
Eligibility	X				
Demographics ^B	X				
Complete Medical History ^C	X	X	X		
Height	X				
Weight	X	X	X	X	
Vital Signs ^D	X	X	X	X	
Complete PE	X	X	X	X	
ECOG PS	X	X	X	X	
12-Lead ECG	X				
CBC with diff	X	X	X	X	
Comp Serum Chemistry Panel ^E	X	X	X	X	
Alpha-fetoprotein (AFP)	X	X	X	X	
Lipase & Amylase	X	(X, repeat only if clinically indicated)			
T3, T4 and TSH	X	X	X	X	
PT/INR, aPTT	X			X	
HBV and HCV Testing	X (Section 12.1)	X (Section 10.2.1)			
Urine or serum pregnancy test ^F	X				
Urinalysis	X				
Correlative Studies: Tissue Sample ^G (Archival or newly obtained)	X				
Correlative Studies: Peripheral Blood ^H (Serum)	X	X ^H	X ^H	X ^H	
Imaging studies ^I	X	(X)	X		
Pembrolizumab IV administration		X			
Baseline Symptoms	X				
Adverse Events			X		(X) ^J
Concomitant Medications			X		
Telephone Call ^L					X

^A Screening evaluations should be done within 28-days prior unless otherwise specified.

^B Demographic data includes age, gender and racial/ethnic background.

^C Complete Medical History includes disease history and prior medical treatments.

^D Vital signs include oral temperature, blood pressure and heart rate.

^E Comprehensive Serum Chemistry Panel includes albumin, alkaline phosphatase, total bilirubin, sodium, calcium, chloride, creatinine, potassium, total protein, AST (SGOT), ALT (SGPT), blood urea nitrogen,.

- ^F Urine or serum (beta-HCG) pregnancy test is required for women of childbearing potential **within 3-days prior to Day 1** of trial treatment.
- ^G Tissue sample (either archival or newly obtained) is optional and for correlative studies (see Section 1.5 and 13.0 for details).
- ^H Serum collection for correlative studies is optional (see Section 1.5 and 13.0 for details). Samples will be collected at baseline, during treatment and/or at the time of documented disease progression, whichever occurs first.
- ^I Imaging studies for tumor assessment for all known sites of disease (including CT or MRI of abdomen with contrast): the same method of assessment and technique used at baseline will be used during treatment and follow-up. Imaging studies will be done every 3 cycles (**after every 9 weeks, ±9 days**) from the date of Enrollment, timed to coincide with the end of the prior treatment cycle.)
- ^J AE/SAE collections should continue for at least 90-days post EoT visit. All subjects with SAEs must be followed up for outcome. (See Section 15.0 and Appendix A for details).
- ^K Follow-up for patients without documented objective disease progression shall occur every 12 weeks (+/- 2 weeks) until documented disease progression, death, withdrawal of consent, or EoS, whichever occurs first.
- ^L Telephone call may be made to patient or patient's family to follow-up on patients' post-study anticancer therapy and survival status. **Following confirmed disease progression or initiation of new anti-cancer therapy, survival will be assessed (at a minimum) by telephone contact every 12 weeks (±2 weeks).**

13.0 SCHEDULE OF CORRELATIVE EVALUATIONS

The following optional samples may be collected (at the discretion of the PI) at the specified time points if the patient consents to them:

13.1 Pre-Treatment Specimen Collection (Screening)

- Tissue sample (archival **or** newly obtained)
- Approximately up to 30 mL peripheral blood (2 green top tubes + 1 red top tube + 1 EDTA tube)

